12.5 Genomic Data Sharing Plan

Not applicable.

13. STATISTICAL CONSIDERATIONS

13.1 Study Design/Endpoints

The primary endpoint is the objective response rate using RECIST 1.1. Tumor response assessed by the local site investigator or delegate will be used to assess the objective response rate. Tumor response will be centrally reviewed by [name] but the local site assessment will be used to determine patient treatment and tumor response outcome.

A Simon minimax sampling two-stage design will be used to estimate the objective response rate with a goal of at least 20% of patients to be considered as having preliminary evidence of activity and less than 5% indicating that trametinib is ineffective as a potential EHE treatment. Thirteen patients with EHE will be enrolled in stage I, and if there is at least one objective response as defined by RECIST 1.1, additional patients with EHE will be enrolled until 27 patients with EHE in which *TAZ-CAMTA1* translocation is detected by fusion FISH in archival tumor tissue have been registered and started treatment. The diagnosis of EHE will be determined by the local site, but the presence of *TAZ-CAMTA1* translocation will be determined by the Cleveland Clinic FISH laboratory. If four or more objective tumor responses are documented among 27 patients with *TAZ-CAMTA1* translocation positive EHE, trametinib will be considered to have activity in EHE. With a type 1 error of 5%, this design will have a power of approximately 80% and will have a 51% probability of terminating after the first step if the response rate is 5%. The ORR, 6-month PFS and 2-year OS rates will be calculated along with their 95% confidence intervals. PFS and OS will be estimated by the Kaplan-Meier method.

In stage I enrollment, the presence of *TAZ-CAMTA1* translocation was not detected in 3 tumor samples and in one case there was insufficient tumor tissue available for the analysis. The rate of *TAZ-CAMTA1* translocation negative EHE is higher than the expected rate of less than 10%, and because we anticipate activation of the MAP kinase pathway to occur in tumor with expression of *TAZ-CAMTA1* but not in tumor without the translocation, the protocol is amended to enroll at least 27 patients with EHE containing *TAZ-CAMTA1* translocation.

Secondary objectives of the 6-month PFS rate, median PFS, and 2-year OS rate will be determined from analyses of patients with *TAZ-CAMTA1* translocation positive EHE. Evaluation of the safety of trametinib, and patient reported symptoms using NIH-PROMIS questionnaires will be determined from analyses of all patients who started treatment with trametinib.

Progression-free survival will be calculated from time of first dose of study medication to occurrence of radiologic tumor progression per RECIST1.1, clinical progression based on treating physician's assessment or death from any cause. Overall survival will be calculated from the time of first dose of study drug to occurrence of death from any cause. Patients who are registered and are determined to be eligible for study treatment but do not start study drug will be replaced. All patients who receive study drug for any period of time will be evaluable for toxicity. The rates of adverse events occurring in at least 5% of subjects and rates of grade 3-5 adverse events will be tabulated by system and term using Common Terminology Criteria of Adverse Events (CTCAE). For dose adjustment schedule see Section 6.1. PROMIS questionnaires will be scored according to recommended standardized system and t-scores generated. A mixed model will be used to analyze change in t-scores over time. Whether or not having evidence of disease progression will be used as a time-dependent variable in the mixed model with adjustment of other potential confounding variables.

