3. PATIENT SELECTION

3.1 Eligibility Criteria

- 3.1.1 Patients must have measurable disease, defined as at least one lesion that can be accurately measured in at least one dimension (longest diameter to be recorded for non-nodal lesions and short axis for nodal lesions) as ≥ 20 mm (≥ 2 cm) with conventional techniques or as ≥ 10 mm (≥ 1 cm) with spiral CT scan, MRI, or calipers by clinical exam. Baseline imaging must be obtained within 30 days of Day 1 of study. See Section 11 for the evaluation of measurable disease.
- 3.1.2 Patients must have histologically confirmed epithelioid hemangioendothelioma which is metastatic or locally advanced (unresectable), and tumor tissue (paraffin-embedded tissue block or tumor tissue on unstained glass slides) available for fusion FISH analysis at Cleveland Clinic. Patient tumor tissue stored in pathology archives may be used for fusion FISH; a new biopsy is not mandatory.

- 3.1.3 Patients must have evidence of disease progression per RECIST1.1 prior to enrollment or have evidence of cancer-related pain requiring symptom management with narcotic analgesics.
- 3.1.4 Because there is no established standard or approved drug therapy for treatment of EHE, patients previously untreated or treated with drug therapy for EHE are eligible. There is no limit on the number of prior regimens used to be eligible.
- 3.1.5 Age ≥ 15 years. EHE is very unlikely to arise before the age of 15 years.
- 3.1.6 ECOG performance status ≤ 2 (Karnofsky $\geq 60\%$, see Appendix A).
- 3.1.7 Life expectancy of greater than 6 months.
- 3.1.8 Able to swallow orally-administered medication and does not have any clinically significant gastrointestinal abnormalities that may alter absorption such as malabsorption syndrome or major resection of the stomach or small bowel.
- 3.1.9 All prior treatment-related toxicities must be CTCAE v5 grade ≤ 1 (**except alopecia**) at the time of enrollment.
- 3.1.10 Patients must have normal organ and marrow function as defined below within 2 weeks of patient registration (for blood results) and 30 days of registration for LVEF assessment:
 - Absolute neutrophil count (ANC) $\geq 1 \times 10^9/L$
 - Hemoglobin ≥ 9 g/dL, patients may receive transfusion to meet criterion
 - Platelets $\geq 75 \times 10^9/L$
 - Albumin ≥ 2.5 g/dL

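### The 4-of-27 rule tests TAZ-CAMTA1 fusion-positive EHE, but success is worded for EHE without that limit

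*Combined protocol and SAP*

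**What the plan says.** All references are to the combined protocol and SAP.

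- **Decision rule (13.1).** The condition opens "If four or more objective tumor responses are documented among 27 patients with" and goes on to name the TAZ-CAMTA1 fusion. The sentence then closes with the conclusion: "translocation positive EHE, trametinib will be considered to have activity in EHE".
- **Hypotheses (13.1).** The upper value is set "with a goal of at least 20% of patients to be considered as having preliminary evidence of activity". The lower value is "less than 5% indicating that trametinib is ineffective as a potential EHE treatment". Neither mentions the fusion.
- **Stage I (13.1).** "Thirteen patients with EHE will be enrolled in stage I, and if there is at least one objective response as defined by RECIST 1.1", the trial continues. This set is not selected on fusion status.
- **Eligibility (3.1.2).** "Patients must have histologically confirmed epithelioid hemangioendothelioma which is metastatic or locally advanced (unresectable"). Tissue must be available for FISH, but a positive result is not required. The primary objective (1.1) has no fusion limit either.
- **Reason for the restriction (13.1).** The fusion was not detected in 3 stage I samples, and one further case had too little tissue. The section refers to the first group as translocation-negative EHE and says its rate is above the expected figure of under 10%. It restricts the final set "because we anticipate activation of the MAP kinase pathway to occur in tumor with expression of" the fusion protein, and not in tumours lacking it.
- **Replacement (13.2).** Each patient whose FISH result is negative, failed or not performed opens one further slot until 27 positives have started treatment.
- **Response analysis (13.5.2).** The main response-rate analysis includes every eligible patient who took at least one dose, whatever the FISH result.

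**The concern.** The final decision rests on one molecular group, and the pre-specified conclusion names the disease. By the protocol's own account the two are not the same: fusion-negative patients have EHE, can enrol, and are replaced because the pathway that the drug targets is not expected to be active in them.

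The error rate of a decision rule belongs to the population whose responses are counted. A positive result would show activity in fusion-positive EHE at the stated error. It would say little about the remainder, yet the success sentence could be read as covering it. In a disease that section 2.1 describes as having no established drug therapy, that reading could carry weight.

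**Working it through.** **1. The plan's own figures.** Let p be the response rate in a homogeneous set, with 13 patients in stage I, 14 more in stage II, and success at 4 or more of 27.

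- Early stop: (1 − p)^13. At p = 0.05 this is 0.95^13 = 0.513.
- Success: the sum over x = 1 to 13 of P[Bin(13, p) = x] × P[Bin(14, p) ≥ 4 − x]. This is 0.0416 at p = 0.05 and 0.801 at p = 0.20.

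The stated 51%, 5% and approximately 80% are reproduced. A full minimax search under the same limits returns the same design.

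**2. Fusion-negative share in stage I.** Assume that the planned 13 were enrolled. One sample was uninformative, so 3/12 = 25%, exact (Clopper-Pearson) 95% CI 5.5% to 57.2%. Out of all 13 it is 3/13 = 23%, CI 5.0% to 53.8%.

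**3. From fusion-positive EHE to all EHE.** Let q be the fusion-negative share. The documents give no response rate for this group; assume 0% to see how far the two claims can separate. Then all-EHE ORR = (fusion-positive ORR) × (1 − q).

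| q | All-EHE ORR if positives are at 20% | All-EHE ORR if positives are at 4/27 = 14.8% |
|---|---|---|
| 10% | 18.0% | 13.3% |
| 3/13 | 15.4% | 11.4% |
| 25% | 15.0% | 11.1% |

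Over the CI for 3/12, the 20% becomes 0.20 × (1 − 0.055) = 18.9% down to 0.20 × (1 − 0.572) = 8.6%.

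**4. Error of the rule if read as a claim about all EHE.** Set the all-EHE ORR at 5%, so that the fusion-positive ORR is 0.05/(1 − q), and keep the 0% assumption. The chance of declaring success depends on how many of the 13 stage I patients were positive, because only they can pass the one-response gate:

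| q | Fusion-positive ORR | 13 positive in stage I | 10 positive | 9 positive |
|---|---|---|---|---|
| 10% | 5.6% | 5.7% | 5.3% | 5.1% |
| 3/13 | 6.5% | 9.1% | 8.4% | 8.1% |
| 25% | 6.7% | 9.7% | 9.0% | 8.7% |

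**5. The same rule read as a fusion-positive claim.** With 10 positives in stage I and non-responding negatives, the error at a fusion-positive ORR of 5% is 3.8% and the power at 20% is 76.9%. With 9 positives they are 3.7% and 75.1%. The error stays under 5%, and power falls slightly because the gate is unselected.

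**The case against.** The best defence is that the sentence discloses its population. Its first half names fusion-positive patients, section 13.1 speaks only of preliminary evidence, and section 2.1 calls the fusion disease-defining and present in more than 90% of EHE tumours. On that view the conclusion means activity in at least the main form of the disease. The disclosure is real, and it keeps this a point of scope, not concealment. It does not settle the matter, because section 13.1 itself counts fusion-negative cases as EHE and says that they were more frequent than expected.

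The size is also open to challenge. If the true share were 10%, 3 or more negatives in 12 would occur with probability 0.11, so stage I does not clearly contradict the protocol's expectation. Diagnosis is made locally, and some negative results may reflect assay or diagnostic error. At a 10% share the excess over 5% is small. These objections stand, and step 4 is therefore an illustration only.

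A reader might go further in four ways that the documents do not support:

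- **That the protocol predicts no response in fusion-negative tumours.** It says only that pathway activation is not anticipated without the fusion (13.1), and that fusion-positive tumours are the likeliest to respond (2.4.1).
- **That fusion-negative patients are wholly left out.** They count at the stage I gate, and 13.5.2 would include them in the main response analysis.
- **That the conclusion was overlooked when the protocol was amended.** The superseded text is not available, so this cannot be checked.
- **That a claim about EHE would be false.** Even with 0% in negatives, positives at 20% give an all-EHE ORR above 5% whenever 0.20 × (1 − q) > 0.05, that is, q below 75%. Likewise, a test of 4 responses against all treated patients is not a protocol rule, so its error is not the trial's error.

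**Conclusion.** The point holds as one of scope: the pre-specified conclusion is wider than the population on which it is decided. The design figures are correct for a homogeneous fusion-positive set and need no change.

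The error under an all-EHE reading, about 5% to 6% at a 10% fusion-negative share and 9% to 10% at 25%, rests on an assumed 0% response in negatives and on a share estimated from 12 samples. If negatives responded as often as positives, no inflation would arise, but the 4-of-27 rule would not show that either. No section plans a response rate for fusion-negative patients; 13.4 reports only how many tumours are positive.

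The conflict between 13.1 and 13.5.2 over the response set is related but separate. Settling it would not by itself correct the success sentence.

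**What to change.** 1. In 13.1, word the success statement and the 5% and 20% hypotheses for TAZ-CAMTA1 fusion-positive EHE, and say that no claim about EHE as a whole will be drawn from the 4-of-27 rule.
2. Add a descriptive table of ORR with exact 95% CI for FISH not detected, for FISH failed or not performed, and for all treated patients.
3. Reconcile 13.1 with 13.5.2: state which set gives the primary ORR and the decision, and label the other as supportive.

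The cost is a few sentences and one table. Under 13.5.2 every patient is already assessed for response, and FISH results are already recorded. Sample size, threshold and stage I gate stay as they are.

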13.2 Sample Size/Accrual Rate

This study will be conducted in a two-stage process. In stage I, 13 patients with EHE will be enrolled. If there is at least 1 objective response, additional patients will be enrolled in stage II until there is evidence that a total of 27 patients with EHE with *TAZ-CAMTA1* translocation detected by fusion FISH have been registered and started treatment. After 27 patients have been enrolled and started treatment, enrollment of additional patients will be held until FISH testing is performed on available tissue from the enrolled patients. One enrollment slot will be opened for each case of FISH result of *TAZ-CAMTA1* translocation "not detected", "test failed", or "test not performed" (no tumor tissue in sample) until a total of 27 patients have enrolled and started treatment with FISH result of *TAZ-CAMTA1* translocation "detected". Enrollment in the second stage will be held until at least 1 objective response has occurred. Enrollment for stage I is anticipated to be complete within the first 12 months of study activation. Enrollment for stage II is anticipated to be complete within 18 months of proceeding to stage II. We anticipate that on average, 1 patient per month will be accrued to the study. The study is open to all eligible persons at least 15 years of age. Because of the very rare nature of the disease under study, we will not restrict enrollment based on sex, race or ethnicity in order to complete accrual within 2-3 years.

PLANNED ENROLLMENT REPORT

Racial Categories	Ethnic Categories				Total
	Not Hispanic or Latino		Hispanic or Latino		
	Female	Male	Female	Male	
American Indian/ Alaska Native	0	0	0	0	0
Asian	1	1	0	0	2
Native Hawaiian or Other Pacific Islander	0	0	0	0	0
Black or African American	3	2	0	0	5
White	9	6	2	1	18
More Than One Race	1	1	0	0	2
Total	14	10	2	1	27

PHS 398 / PHS 2590 (Rev. 08/12 Approved Through 8/31/2015)

OMB No. 0925-0001/0002

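### The roughly 80% power in 13.1 is that of a one-population Simon design; under the amended rule it is about 75% to 77% if patients without a detected fusion respond at 0% to 5%

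*Combined protocol and SAP*

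**What the plan says.** Section 13.1 names the design: "A Simon minimax sampling two-stage design will be used to estimate the objective response rate". The target is "a goal of at least 20% of patients to be considered as having preliminary evidence of activity", and the null is "less than 5% indicating that trametinib is ineffective as a potential EHE treatment". The gate is "Thirteen patients with EHE will be enrolled in stage I, and if there is at least one objective response as defined by RECIST 1.1". It has no fusion requirement, and 13.2 repeats it: "In stage I, 13 patients with EHE will be enrolled".

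The final rule counts a different set of patients: "If four or more objective tumor responses are documented among 27 patients with" a detected translocation. Straight after it comes the statement of properties: "With a type 1 error of 5%, this design will have a power of approximately 80% and will have a 51% probability of terminating". The last of these figures refers to the end of stage I, at a response rate of 5%.

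The next paragraph of 13.1 reports that in stage I the "translocation was not detected in 3 tumor samples and in one case there was insufficient tumor tissue available for the analysis". It explains the amendment to 27 fusion-positive patients by the expectation that the MAP kinase pathway is active in tumours with the fusion and not in those without. Section 13.2 opens a replacement slot for each result that is not detected, failed or not performed, so none of the four counts among the 27.

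**The concern.** A Simon calculation assumes that stage I patients are the first part of the sample on which the verdict is reached, all with the same response rate. After the amendment, four of the 13 gate patients are outside the tested population. If they are unlikely to respond, as the amendment's rationale suggests, the gate has fewer chances to open when the drug works in fusion-positive disease. An active drug is then stopped more often than the one-population calculation implies. The gate can also be opened by a response that never counts in the verdict. A reader of a negative result would credit the trial with more power than it has, on the sentence that defines the primary decision.

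**Working it through.** **Inputs.** From 13.1: null 5%, target 20%; gate of at least 1 response in 13; success at 4 or more of 27. FISH-detected patients in stage I: 13 − 3 − 1 = 9, so 27 − 9 = 18 come later. The response rate q in the other four is not given. I take 0% to 5% from the protocol's rationale, with 10% and 20% as sensitivity values.

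**The plan's own figures.** With p the response rate, a one-population trial succeeds unless it has fewer than 4 of 27 or is stopped with 0 of 13:

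P(success) = P(Bin(27,p) ≥ 4) − (1−p)^13 × P(Bin(14,p) ≥ 4)

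- p = 0.20: 0.8177 − 0.0550 × 0.3018 = 0.801
- p = 0.05: 0.0437 − 0.5133 × 0.0042 = 0.0416
- Early stop at 5%: 0.95^13 = 0.513; at 20%: 0.80^13 = 0.055

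So the stated power and early-stop probability reproduce, and the 5% type I error holds as an upper bound. A search over two-stage designs confirms this as the minimax design for these inputs.

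**The amended rule.** The trial stops only if none of the 9 positives and none of the other four respond. Let M be the chance that none of the four responds; with a common rate, M = (1−q)^4. Then:

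P(success) = P(Bin(27,p) ≥ 4) − (1−p)^9 × M × P(Bin(18,p) ≥ 4)

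At p = 0.20 this is 0.8177 − 0.1342 × M × 0.4990, and the chance of stopping at the gate is 0.1342 × M.

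| Other four stage I patients | M | Power | Stop at gate, positives at 20% |
|---|---|---|---|
| all at 0% | 1.000 | 75.1% | 13.4% |
| all at 5% | 0.815 | 76.3% | 10.9% |
| all at 10% | 0.656 | 77.4% | 8.8% |
| all at 20% | 0.410 | 79.0% | 5.5% |
| untestable at 20%, three negatives at 0% | 0.800 | 76.4% | 10.7% |
| untestable at 20%, three negatives at 5% | 0.686 | 77.2% | 9.2% |

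**Under the null (positives at 5%).** Type I error = 0.0437 − 0.6302 × M × 0.0109. This is 3.7% at q = 0 and 4.1% at q = 20%. Early stop is 0.95^9 = 63.0% at q = 0 and 0.95^13 = 51.3% at q = 5%.

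**Which responses open the gate.** If all 13 respond at 5%, the chance of continuing with no response among the nine positives is 0.6302 × (1 − 0.8145) = 0.117. That is 24% of the total chance of continuing (0.117 / 0.487).

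**Conditional on passing the gate** (positives at 20%): at q = 0, 0.751 / (1 − 0.134) = 86.7%; at q = 20%, 0.790 / (1 − 0.055) = 83.6%.

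**The case against.** The strongest reply is that the loss of 3 to 5 points rests on a response rate the documents do not give. An expectation about pathway activation is not a response rate, and at 20% in the other four the power is 79.0%, which fits a figure called approximate. This stands as a limit: the lower power must carry its assumption. It does not rescue the sentence, because a 20% rate in patients without the fusion runs against the reason given for the amendment.

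A second reply is that the calculation fixes the observed stage I mix while treating the same patients' responses as unknown. That is fair. The documents do not say whether the gate had been passed when the amendment was written, and once it is passed the remaining rule has 83.6% to 86.7% power for q between 0% and 20%. The stated 80% is itself an unconditional design property, so the unconditional figure is the like-for-like comparison, but it should be labelled.

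A reader might also infer several stronger things that the documents do not support:

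- **That the 51% is wrong.** The gate is still one response in 13, and 13.1 attaches the figure to a 5% response rate. It holds if all 13 respond at 5%.
- **That 13.1 misstates the risk of stopping an active drug.** It gives no stopping probability at 20%; the 5.5% comparator is calculated here.
- **That type I error is inflated.** It stays at or below 4.1% across the rates examined, and would be 4.4% with no gate at all.
- **That the untestable patient might count as a tenth positive.** Sections 13.1 and 13.2 require a detected FISH result and replace that patient. A likely positive status can matter for the gate only, as in the last two rows of the table.
- **That the amendment cost power.** If the others cannot respond, a verdict on 27 mixed patients after the same gate would have less power, since fewer than 27 could respond. The loss comes from the make-up of stage I.

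**Conclusion.** The stated power does not describe the rule to which it is attached. With 9 of 13 stage I patients FISH-detected and a 20% response rate in positives, unconditional power is about 75% to 77% if patients without a detected fusion respond at 0% to 5%. That range includes the case where the untestable patient responds at 20%. Power is about 79% if all four respond at 20%. The early-stop probability with positives at 5% runs from 51% to 63%, depending on the same assumption. The count of nine assumes that stage I was exactly 13 patients and that all but the four reported were detected. This corrects a stated figure; the decision rule and its control of false positives remain valid.

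**What to change.** In 13.1, replace the power sentence with the properties of the amended rule:

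- 9 of the 13 stage I patients FISH-detected;
- type I error about 4%;
- power about 75% to 77% at a 20% response rate in positives, assuming 0% to 5% in patients without a detected fusion, and about 79% if they too respond at 20%;
- early stop 51% to 63% with positives at 5%.

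Say that these figures are unconditional on passing the gate. Report whether the response that opens, or opened, stage II was in a FISH-detected patient.

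The cost is one paragraph and a stated power a few points less favourable. No patients, thresholds or procedures change.

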2.2.1.3 Trametinib Safety Profile

A Comprehensive Adverse Events and Potential Risks (CAEPR) list using NCI Common Terminology Criteria for Adverse Events (CTCAE) terms is included in Section 7.1 of the protocol.

Based on available AE data from clinical studies involving trametinib to date, the most common toxicities are rash and diarrhea. Rash and diarrhea are common, class-effect toxicities for MEK inhibitors. In addition, visual impairment and left ventricular ejection fraction (LVEF) reduction, although observed at lower frequencies, are also considered class-effect toxicities as they have been observed with trametinib as well as other MEK inhibitors.

AEs of special interest:

Rash, diarrhea, visual disorders, hepatic disorders, cardiac-related AEs, and pneumonitis are considered AEs of special interest because they are either known class effects (*i.e.*, have been observed with other MEK inhibitors) or are potentially life-threatening (Investigator's Brochure, 2013). The following sections provide integrated summaries for these AEs across different clinical trials, with emphasis on trials using trametinib as monotherapy, especially at the RP2D of 2 mg.

Refer to dose modification guidelines for the toxicities for which they are addressed in Section 6.

Rash: Rash was a common AE observed across different dose levels and in different combinations (Investigator's Brochure, 2013). At the 2 mg dose, rash was seen in 27% to 78% of patients in different trials. Of the ~370 subjects with rash AEs at the 2 mg monotherapy dose (including crossover subjects) in five studies, the majority of rash AEs were grades 1 or 2 (24% to 73%); 0% to 9% of patients experienced grade 3 rash AEs, and four patients had a grade 4 rash AE.

In a randomized phase 3 trial of trametinib vs. chemotherapy, the overall incidence of skin toxicity (including rash, dermatitis, acneiform rash, palmar-plantar erythrodysesthesia syndrome, and erythema) was 87% in patients treated with trametinib and 13% in chemotherapy-treated patients. Severe skin toxicity occurred in 12% of patients on the trametinib arm, most commonly for secondary infections of the skin. The median time to onset of skin toxicity was 15 days (range: 1 to 221 days), and median time to resolution was 48 days (range: 1 to 282 days). Dose reduction was required in 12% for skin toxicities, and permanent discontinuation of trametinib was required in 1% of patients.

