6.1.6 Trametinib Dose Modification for Pneumonitis

Pneumonitis has been observed in patients receiving trametinib. To reduce the risk of pneumonitis, patients will be monitored closely for symptoms and evaluated with imaging and functional tests. Dose modification and supportive care guidelines for pneumonitis are described in the tables below.

Pneumonitis Guidelines for Trametinib Monotherapy		
CTCAE Grade	Adverse Event Management	Action and Dose Modification
Grade 1	
 • CT scan (high-resolution with lung windows) recommended. • Work-up for infection • Monitoring of oxygenation via pulse-oximetry recommended • Consultation with pulmonologist recommended 	
 • Continue trametinib at current dose
Grade 2	
 • CT scan (high-resolution with lung windows) recommended. • Work-up for infection • Consult pulmonologist • Pulmonary function tests – if < normal, repeat every 8 weeks until \geq normal • Bronchoscopy with biopsy and/or BAL recommended • Symptomatic therapy including corticosteroids if clinically indicated 	
 • Permanently discontinue trametinib if pneumonitis is related to treatment.
Grade 3	
 • Same as grade 2 	
 • Permanently discontinue trametinib
Grade 4	
 • Same as grade 2 	
 • Permanently discontinue trametinib

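### With 21 to 40 treated patients, the 5% cut in the adverse-event tables means two patients per term, so a grade 1-2 event in one patient is left out of the planned safety output even when it ended treatment

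*Combined protocol and SAP*

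**What the plan says.** Section 13.1 gives the tabulation rule: "The rates of adverse events occurring in at least 5% of subjects and rates of grade 3-5 adverse events will be tabulated", by body system and CTCAE term. Safety results "will be determined from analyses of all patients who started treatment with trametinib", whether or not the fusion is detected, and any exposure is enough: "All patients who receive study drug for any period of time will be evaluable for toxicity". Section 13 plans no table of SAEs, of adverse events leading to discontinuation, or of events of special interest; section 13.5.1 only defines who is evaluable for toxicity.

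Section 2.2.1.3 singles out six groups: "Rash, diarrhea, visual disorders, hepatic disorders, cardiac-related AEs, and pneumonitis are considered AEs of special interest". Section 6 attaches firm consequences to some of these below grade 3. For grade 2 pneumonitis, section 6.1.6 says: "Permanently discontinue trametinib if pneumonitis is related to treatment". Sections 6.1.3 and 6.1.7 have similar rules for retinal and ejection-fraction events.

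Section 7.4 requires all adverse events to be reported in routine data. Section 12.1 keeps a running list of reasons for drug discontinuation and of SAEs, for review on conference calls.

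**The concern.** Evaluating safety is a secondary objective (section 1.2), and section 2.2.1.2 says that trametinib has had no formal evaluation in this disease or in soft tissue sarcoma. In a large trial a 5% cut keeps tables readable. In a trial of about 30 patients it is a rule about one patient versus two.

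The grade 3-5 table catches severe events at any frequency, but the protocol also treats some lower-grade events as grave enough to stop treatment or file an SAE. If such an event occurs once, a report that follows 13.1 to the letter has no row for it. A reader of the tables would then not see why that patient stopped.

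**Working it through.** **Number treated.** The design starts from 13 patients in stage I (section 13.2: "In stage I, 13 patients with EHE will be enrolled") and continues until 27 patients with a detected fusion have started treatment. The design figures behind those numbers reproduce. With at least one response in 13 needed to continue and four or more in 27 for activity, the exact two-stage binomial gives type 1 error 0.042, power 0.801 and early-stopping probability 0.95^13 = 0.513, against the stated 5%, about 80% and 51%.

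Section 13.1 reports three stage I tumours without a detected fusion and one with too little tissue. These four do not count towards the 27. Assuming all four were treated, the safety set is at least 27 + 4 = 31. If the stage I yield of 9 in 13 persisted, it would be about 27/(9/13) = 39.

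**What 5% means in patients.** The smallest qualifying count is 0.05 x N, rounded up.

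| N treated | 1/N | 2/N | Patients needed |
|---|---|---|---|
| 13 | 7.7% | 15.4% | 1 |
| 20 | 5.0% | 10.0% | 1 |
| 21 | 4.8% | 9.5% | 2 |
| 27 | 3.7% | 7.4% | 2 |
| 31 | 3.2% | 6.5% | 2 |
| 40 | 2.5% | 5.0% | 2 |
| 41 | 2.4% | 4.9% | 3 |

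From 21 to 40 treated, the cut therefore removes exactly those terms seen in one patient at grade 1-2. A trial that ended with 20 or fewer treated would not have the problem.

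**Events below grade 3 with a stopping or SAE rule.**

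- Grade 2 pneumonitis related to treatment: permanent discontinuation (6.1.6).
- Retinal vein occlusion found on work-up of a grade 1 or 2 visual change: permanent discontinuation and SAE (6.1.3).
- Retinal pigment epithelial detachment: SAE when diagnosed; at grade 2-3 without recovery in four weeks, permanent discontinuation (6.1.3).
- Asymptomatic ejection-fraction fall of more than 10 points to below the institutional limit, not recovered in four weeks: permanent discontinuation and SAE (6.1.7). The same table sets grade 3 at 39-20% or a fall of more than 20 points, so a smaller fall is below grade 3.

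**Chance of a single case.** P(exactly one) = N x p x (1 - p)^(N - 1). The rates p are assumed; 4% is the top of the 0% to 4% range that section 2.2.1.3 cites for pneumonitis at 2 mg. This figure covers any grade, so the chance of omission is P(exactly one) multiplied by the chance that the case is grade 1-2. Two splits come from section 2.2.1.3: pneumonitis, 3 of 9 at grade 1-2 (0.333); visual disorders, 85 subjects less 7 at grade 3-4, so 78/85 (0.918).

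| True rate p | P(exactly one), N = 27 | P(exactly one), N = 31 | N = 31, x 3/9 | N = 31, x 78/85 |
|---|---|---|---|---|
| 1% | 0.208 | 0.229 | 0.076 | 0.210 |
| 2% | 0.319 | 0.338 | 0.113 | 0.310 |
| 3% | 0.367 | 0.373 | 0.124 | 0.342 |
| 4% | 0.374 | 0.364 | 0.121 | 0.334 |

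With 31 treated, the chance of omission is about 8% to 12% with the pneumonitis split and about 21% to 34% for a term as predominantly low grade as the pooled visual disorders. The second split is an illustration: it pools many visual terms, and no grade split is given for retinal vein occlusion or epithelial detachment alone.

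**The case against.** The sentence in 13.1 says what will be tabulated; it does not forbid listings or SAE narratives. All adverse events are recorded, and discontinuation reasons and SAEs are reviewed on calls that include the statistician. A frequency cut combined with all grade 3-5 events is a common format. The agent's profile rests on far more data than this trial will add: the risk list in section 7.1 uses 1111 patients, and section 2.2.1.2 expects adverse-event rates much like those in melanoma and lung cancer. Nothing here touches the primary endpoint or its decision rule.

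Most of that stands, and it limits the point. What it does not do is supply a planned output: the running list in 12.1 is an oversight tool, and section 13 names no table or listing that would carry these events into the report.

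A reader might infer more than the documents support:

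- **That the events are lost.** They are not. They remain in the data and, where applicable, in SAE reports.
- **That the 23% to 37% range is the chance of omission.** It covers a single case of any grade. For pneumonitis, six of the nine cited cases were grade 3 and would be tabulated at any frequency.
- **That the filter removes the special-interest risks in general.** The ranges cited at 2 mg lie largely above the cut: rash 27-78%, diarrhea 33-58%, hepatic 8-34%, visual 4-21%, cardiac 3-21%. Individual terms within a category can be rarer, but the realistic loss is narrow.
- **That splitting related terms always hides events.** Heart failure and decreased ejection fraction are separate terms in section 7.1, and one case of each would both be omitted only if both were grade 1-2. The symptomatic row in 6.1.7 lists only grades 3 and 4, which are tabulated.

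**Conclusion.** The point holds as a gap in the planned safety tables. It rests on three things: stage II completes with 21 to 40 treated (at least 31 if the four stage I patients without a detected fusion were treated), the 5% rule is applied term by term as 13.1 says, and no adverse-event output is planned beyond that sentence.

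The content at risk is small but not trivial: isolated grade 1-2 cases of pneumonitis, retinal vein occlusion, retinal pigment epithelial detachment or ejection-fraction decline, some of which end treatment under the protocol's own rules. It is worth correcting because safety is a secondary objective and this cut shortens the table only by removing single-patient, low-grade terms. It gives no reason to doubt safety data collection, patient monitoring or the efficacy conclusion.

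**What to change.** In section 13.1, keep the existing tables and add, regardless of grade and frequency, a table or listing of:

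- every adverse event leading to dose interruption, dose reduction or permanent discontinuation;
- every SAE;
- every event in the special-interest groups of section 2.2.1.3, with related terms grouped (for example the cardiac terms that section 7.1 lists separately).

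The alternative is to drop the 5% cut and tabulate all adverse events by system, term and worst grade. Either change closes the gap.

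The cost is a sentence or two in the plan and a longer table. Section 7.4 already requires all adverse events to be reported, so no new data are needed.
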